Poor adherence to buprenorphine treatment has been associated with a number of negative outcomes including poor treatment retention of patients participating in office based treatment (Matson et al. 2014). Compared to patients with good adherence, poorly adherent patients in office based buprenorphine treatment were ten times more likely to relapse to opioid use (Tkacz et al. 2012).

The growth in cell phone use creates an unprecedented opportunity to improve medication adherence (Krishna, Boren, and Balas 2009; Lester et al. 2010; Horvath et al. 2012; Granholm et al. 2011; Pop-Eleches et al. 2011). The use of Remote Observed Dosing (ROD) allows us to reach underserved, at-risk populations (Hoffman et al. 2010). In a study with cannabis dependent patients using ROD that was directly observed (DOT) over Skype for three weeks, every morning 20 participants were video called by staff who observed consumption of the study medication. Adherence was confirmed 96% of the time and was also assessed with weekly face-to-face visits, pill counts, and plasma drug levels (DeWorsop et al. 2016).

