## 2 Study Objectives

ROD has the potential to 1) improve adherence, 2) reduce the risk of diversion, and 3) increase access to buprenorphine treatment.

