Hamilton Depression Rating Scale (Hamilton 1967). The Ham-D is a 20-minute, 24-item interview that measures the severity of depression and changes in depressive symptoms. The Ham-D is administered at baseline, week 9 and at the end of the study.

Locator Form. The locator form asks about addresses and phone numbers where the participant might be contacted, as well as names and addresses of other individuals who might know the participant's whereabouts. The information is used to locate participants who do not respond to a calls and weekly text messages.

Obsessive Compulsive Drug Use Scale (Franken, Hendriks, and van den Brink 2002). Adapted from the Obsessive Compulsive Drinking Scale(Anton, Moak, and Latham 1995) (OCDS), measures craving for heroin on a 12-item likert scale. Our version replaces heroin with opioids more generally. This will be administered at baseline and weekly throughout the trial.

Risk Assessment Battery (Metzger et al. 1993). The RAB is a 38 item self-report questionnaire which assesses high risk behavior for exposure to the HIV virus. The RAB yields drug, sex and total risk scores and will be administered at baseline and at the end of the trial.

Systems Usability Scale (Grindrod, Li, and Gates 2014). The SUS is a 10 item self-reported validated measure of learnability and user satisfaction that we will use to evaluate the remote medication monitoring protocol. It uses a 5-point Likert scale to provide a quantitative measure of the usability of the ROD protocol and provides an overall score between 0 and 100. This scale will be administered at the end of the study.

Timeline Follow Back Interview (Sobell and Sobell 1995). The TLFB is a 15-30 minute, semi-structured interview adapted by our laboratory to collect information about daily drug, alcohol, and nicotine use. The TLFB will be given by trained research staff at baseline to cover 3 months immediately preceding treatment entry and will be updated at each research visit to determine any time spent in a controlled environment and cocaine, nicotine, and other drug use during the

CONFIDENTIAL

period since the last visit. The composite of these assessments are additive over the course of the study so that we will have continuous data.

Video Compliance. Submission of videos will be recorded (date and time) and assessed daily for compliance (i.e., taking the medication as prescribed). In addition, videos will be saved off the micro-SD cards at each office visit.

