### **Laboratory Measurements (in alphabetical order)**

Blood chemistry, Complete Blood Count (CBC), and Urinalysis are obtained to assess for adverse events. Enzyme levels will be obtained once at baseline and end of the study.

Pregnancy Testing. Urine pregnancy tests will be obtained from all women at baseline, week 5, week 9, and end of study.

Urine Drug Screen and Urine Buprenorphine and Norbuprenorphine Screen. Quantitative urine buprenorphine and norbuprenorphine levels (using gas chromatography) with urine creatinine used as a control for urinary concentration will be assessed twice weekly throughout the trial. Urinary buprenorphine levels have been used extensively to establish buprenorphine adherence (Fox, Tetlow, and Allen 2006; Vincent et al. 1999). Quantitative levels of methadone have been used successfully to establish methadone compliance in a methadone maintenance program (Preston et al. 2003). Our toxicology consultant will assist us in interpreting urine creatinine controlled quantitative buprenorphine levels to establish medication adherence. Data from this trial will be used in optimizing the use of quantitative urine buprenorphine and norbuprenorphine levels in the subsequent efficacy trial. Qualitative (emit) urine toxicology for other drugs (benzodiazepines, barbiturates, opiates, marijuana, methadone, and amphetamine) is done at baseline and weekly throughout the trial.

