## **3.4 Study Endpoints**

### **3.4.1 Primary Study Endpoint**

For the ROD group, we will calculate the within-patient proportion of study days on which video captured adherence, as per protocol.

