### **Secondary Study Endpoints**

We will use a combination of self-report and (nor)buprenorphine levels to classify patients in the AC group as adherent or non-adherent for each study day to compare their rates of adherence to the (video-verified) rates in the ROD group. These comparisons will give a direct estimate of the improvement in adherence likely to be observed between the proposed method and standard methods.

Rates of illicit opiate use will be compared between the groups using combinations of urine drug screens (UDS) and TLFB self-reports obtained at each visit.

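### A ROD day is adherent on video alone while AC days and one benchmark rate use urine, so doses filmed but not absorbed can favour ROD

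*Combined protocol and SAP*

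**What the plan says.** **ROD days.** Section 3.4.1 scores the ROD group by the "within-patient proportion of study days on which video captured adherence, as per protocol". Sections 2.1, 5.6 and 6.2 repeat this definition, and none of them adds a urine condition. Section 3.3 describes the video measure: "Submission of videos will be recorded (date and time) and assessed daily for compliance (i.e., taking the medication as prescribed"). It adds that videos are also copied from the phones' micro-SD cards at office visits.

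**Urine.** Both groups give quantitative buprenorphine and norbuprenorphine samples. Under Laboratory Measurements in 3.3 these "will be assessed twice weekly throughout the trial", and Table 1 schedules 24 of them in weeks 3-14. The same paragraph states that "Urinary buprenorphine levels have been used extensively to establish buprenorphine adherence" and that "Our toxicology consultant will assist us in interpreting urine creatinine controlled quantitative buprenorphine levels to establish medication adherence". It gives no cut-off or detection window, and it does not link a sample to a ROD day.

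**AC days.** The secondary endpoints use a "combination of self-report and (nor)buprenorphine levels to classify patients in the AC group as adherent or non-adherent for each study day", and set the result against the video-verified ROD rate. Sections 5.6 and 6.2 say the same; 6.2 labels the comparison exploratory and assigns it a mixed effects logistic model.

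**Prior rates.** Section 6.2 also compares the ROD rate with three published studies. Section 1.1 describes one of them (50 office-based patients, 48% adherent) as defining adherence by buprenorphine-positive urine at 80% or more of visits.

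**Urine as an outcome.** Sections 6.2 and 6.3.2 make creatinine-normalised levels in both groups the primary between-group comparison, analysed by linear mixed models.

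**The concern.** Daily review should reject a video in which the dose is visibly not taken. It cannot reject a dose that looks taken and is then removed, and patients hold a week's supply at a time (5.2.3). Diversion is part of the trial's rationale: section 2 lists the potential to "reduce the risk of diversion" among the aims of ROD. The plan also treats drug levels as evidence of adherence elsewhere. Section 1.1 reads the all-positive urines of the team's own feasibility study as a sign of adherence. It also notes that in the cited video-call study of cannabis-dependent patients adherence "was also assessed with weekly face-to-face visits, pill counts, and plasma drug levels".

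Two comparisons are at stake. In the daily comparison, urine is one of the inputs that can count against an AC day but can never count against a ROD day. The secondary-endpoint text nevertheless presents the result as a direct estimate of the gain in adherence. In the comparison with prior studies, a video-only rate is set against at least one rate defined by urine. In both, a dose filmed but not absorbed pushes the result in favour of ROD.

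**Working it through.** **1. The plan's own figure.** Section 6.1 gives 95% intervals for the share of 20 ROD patients adherent on at least 80% of days: (68%, 98%) at 90% and (72%, 99%) at 95%. The method is not stated. An interval on the log-odds scale, logit(p) ± 1.96/√(np(1−p)), comes closest:

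- 18/20: logit 2.197 ± 1.96 × 0.745 gives (67.6%, 97.5%).
- 19/20: logit 2.944 ± 1.96 × 1.026 gives (71.8%, 99.3%).

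Three bounds agree after rounding and the fourth is about half a point away. These intervals are not in dispute. They take each patient's video classification as correct.

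**2. Inputs for the illustration.** 84 video days and 24 urine samples in weeks 3-14 (Table 1); 20 ROD patients (section 3); an 80% threshold (6.1). The number of discordant samples, k, is an assumption, because the documents give no rate.

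**3. Days per sample.** 84/24 = 3.5 on average, if each sample answers for the days since the one before.

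**4. Effect on one patient.** With a share f of days filmed, spread evenly over the sampling intervals, the corroborated proportion is f × (1 − k/24).

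| Filmed share f | Largest k still at 80% or more | Smallest k below 80% |
|---|---|---|
| 100% | 4: 20/24 = 83.3% | 5: 19/24 = 79.2% |
| 95% | 3: 0.95 × 21/24 = 83.1% | 4: 0.95 × 20/24 = 79.2% |
| 90% | 2: 0.90 × 22/24 = 82.5% | 3: 0.90 × 21/24 = 78.8% |

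For the fully filmed patient, five samples are 5 × 3.5 = 17.5 days, and (84 − 17.5)/84 = 79.2%.

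**5. Effect on the group share.** Each patient who crosses the line moves the ROD share by 1/20 = 5 points. Starting from 18/20 and using the same interval method:

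- one patient reclassified: 17/20 = 85% (62%, 95%);
- two patients reclassified: 16/20 = 80% (57%, 92%).

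**6. Which analyses could absorb the problem.**

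| Analysis | Evidence for ROD | Evidence for the comparator |
|---|---|---|
| 3.4.1 proportion and 80% share (6.1) | Video | None |
| Daily comparison with AC | Video | Self-report and urine |
| Prior study with 48% adherent | Video, by day | Urine, by visit |
| Primary between-group model (6.3.2) | Urine levels | Urine levels |

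Only the last row treats both sides alike. It compares levels between the groups and returns no corrected adherence proportion, so it repairs none of the first three.

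**The case against.** A reader might infer that the plan throws away objective evidence. It does not: urine levels in both groups are the primary between-group comparison and the basis of the power statement in 6.1. Widespread non-absorption in the ROD group could show there.

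A reader might also infer that the video measure can only err upward. That holds for the one mechanism considered here. A dose taken but not filmed or not sent lowers the same proportion, so the net direction of error is unknown.

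Nor do the documents say that the video shows only the placing of the medication. Reviewers judge whether it was taken as prescribed, although the detailed criteria are not given. The cited video-call study assessed drug levels alongside observation, and nothing suggests that they overruled it.

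The case against making a urine override the primary endpoint is sound as the plan stands. There is no cut-off, detection window or rule for missing urine. Section 3.3 says this trial's data will help optimise the use of quantitative levels in the subsequent efficacy trial. One spot sample would reclassify several days, and a patient who diverts some doses but takes others could still test positive. The feasibility study's all-positive urines suggest that discordance may be rare, although those doses were watched live on weekdays with a weekly dose in the office.

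These arguments limit the remedy. They do not explain why urine should bear on AC days and not on ROD days, and they supply no rule for a video and a urine result that disagree.

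**Conclusion.** The gap is real and of moderate importance. Video alone decides a ROD day in the primary endpoint, the daily comparison with AC and the comparison with prior studies. AC days and one of the prior rates draw on urine. Doses that look taken on film but are not absorbed would raise the ROD rate and favour ROD, and the separate urine model does not correct this.

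The size is sensitivity arithmetic, not a forecast. Five discordant samples of 24 take a fully filmed patient from 100% to 79%, and each patient who crosses 80% moves the ROD share by 5 points. This rests on an average of 3.5 days per sample, on each sample covering the days since the last, and on an 80% line that 6.1 offers as an example; the 3.4.1 endpoint itself is a continuous proportion. The documents do not support reading this as evidence that ROD patients divert doses, or as a reason to abandon the video measure.

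**What to change.** Keep the video proportion as defined. Prespecify beside it a urine-corroborated ROD proportion. A day with a compliant video, uploaded or recovered from the micro-SD card, would not count when the sample covering it shows no norbuprenorphine. Use this version for the comparison with AC, with the same sample rule on AC days, and for the comparison with the urine-based prior rate. The latter match is closer but not exact, because that study counted visits. Report video-urine agreement per sample.

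Before analysis, fix with the toxicology consultant:

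- the assay cut-off;
- the days each sample covers, with a cap when a visit is missed;
- the handling of missing urines.

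The cost is a paragraph of endpoint text and a small programming step; no new data are needed. An occasional false-negative urine would remove about 3 to 4 days, or up to about 7 after a missed visit if no cap is set. Partial diversion with a positive urine would stay undetected.

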### **Secondary Study Endpoints**

We will use a combination of self-report and (nor)buprenorphine levels to classify patients in the AC group as adherent or non-adherent for each study day to compare their rates of adherence to the (video-verified) rates in the ROD group. These comparisons will give a direct estimate of the improvement in adherence likely to be observed between the proposed method and standard methods.

Rates of illicit opiate use will be compared between the groups using combinations of urine drug screens (UDS) and TLFB self-reports obtained at each visit.

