### 2.1 Primary Objective

- The overarching aim of this behavioral intervention is to test the preliminary efficacy of using remote adherence monitoring in buprenorphine (Suboxone®) treatment for OUD. For the ROD group, we will calculate the within-patient proportion of study days on which video captured adherence, as per protocol. We will use these data to compare observed adherence rates in this group to rates reported in prior studies and to the attention control group.

CONFIDENTIAL

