#### **5.6 Efficacy Evaluations (only if applicable)**

For the ROD group, we will calculate the within-patient proportion of study days on which video captured adherence, as per protocol.

We will use a combination of self-report and (nor)buprenorphine levels to classify patients in the AC group as adherent or non-adherent for each study day to compare their rates of adherence to the (video-verified) rates in the ROD group. These comparisons will give a direct estimate of the improvement in adherence likely to be observed between the proposed method and standard methods.

Rates of illicit opiate use will be compared between the groups using combinations of urine drug screens (UDS) and TLFB self-reports obtained at each visit.

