## **6.2 Statistical Methods**

For the ROD group, we will calculate the within-patient proportion of study days on which video captured adherence, as per protocol. We will use these data to compare observed adherence rates in this group to rates reported in prior studies. The primary comparison between the groups will use the creatinine normalized weekly quantitative urine levels for buprenorphine and norbuprenorphine. Exploratory analyses include the following: We will use a combination of self-report and (nor)buprenorphine levels to classify patients in the AC group as adherent or non-adherent for each study day, and use mixed effects logistic regression models to compare their rates of adherence to the (video-verified) rates in the ROD group. Rates of illicit opiate use will be compared between the groups using combinations of urine drug screens(UDS) and TLFB self-reports obtained at each visit. The ASI, CGI, and HAM-D scales are obtained monthly. To assess usability and acceptability of the ROD protocol and text messaging application, [name] will conduct semi-structured interviews and analyze data from the Systems Usability Scale (SUS) at the final office visit.

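### The adherence-rate comparison scores ROD by video and control by self-report plus urine, so it cannot separate a treatment effect from a difference in measurement

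*Combined protocol and SAP*

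**What the plan says.** **ROD arm.** The primary endpoint (3.4.1) is the "within-patient proportion of study days on which video captured adherence".

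**Attention control (AC) arm.** Dosing is not observed. Sections 3.4, 5.6 and 6.2 combine self-report with buprenorphine and norbuprenorphine levels. Section 3.4 states the use: "classify patients in the AC group as adherent or non-adherent for each study day to compare their rates of adherence to the (video-verified) rates". Section 6.2 will "use mixed effects logistic regression models to compare their rates of adherence to the (video-verified) rates in the ROD group". Sections 3.4 and 5.6 conclude: "These comparisons will give a direct estimate of the improvement in adherence likely to be observed between the proposed method and standard methods".

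**Status of the contrast.** The primary objective (2.1) is to "compare observed adherence rates in this group to rates reported in prior studies and to the attention control group". Section 3.4 lists the contrast as a secondary endpoint. Section 6.2 places it under a different heading: "Exploratory analyses include the following: We will use a combination of self-report and (nor)buprenorphine levels to classify patients in the AC group".

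**What is measured in both arms.** Quantitative urine levels are taken twice weekly in everyone, and on these section 6.2 says: "The primary comparison between the groups will use the creatinine normalized weekly quantitative urine levels". On interpretation, section 3.3 says: "Our toxicology consultant will assist us in interpreting urine creatinine controlled quantitative buprenorphine levels to establish medication adherence".

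**The concern.** No ROD day is scored by the AC rule and no AC day by the ROD rule. The group coefficient is therefore the sum of an arm effect and an instrument effect, and a larger sample would not pull them apart. Nothing in the plan calibrates video against urine or examines misclassification.

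The errors also fall on different arms. A dose taken but not filmed counts against ROD only. Saving videos from the phone cards (3.3) can recover a failed upload but not an unfilmed dose. A dose confirmed but not taken can count in favour of AC only. A strict AC rule would push the other way. The rule for combining self-report and urine is not given, nor is the source of the self-report. The daily confirming text (3.1) is one candidate; the Timeline Follow Back is described as covering drug, alcohol and nicotine use, not study doses. The direction of bias is therefore open.

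At stake is the size of effect that readers take from this trial. Section 3.3 anticipates a later efficacy trial, and a measurement artefact could be carried into it as the expected gain.

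**Working it through.** **The plan's own figures.** The protocol gives no expected rate, power or interval for this contrast. The figures in section 6.1 concern other quantities, and they reproduce:

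- *Urine levels, 80% power at d = 0.65.* I get 0.801 with 20 per arm, within-subject correlation 0.4 and alpha 0.05. My assumptions are two-sided testing, 12 weekly measures, compound symmetry and dropout rising linearly to 10%.
- *ROD-only intervals.* Logit intervals are 67.6% to 97.5% for 18/20 (stated 68%, 98%) and 71.8% to 99.3% for 19/20 (stated 72%, 99%).

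None of these changes.

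**How much urine stands behind the AC score.** Table 1 has 84 monitoring days and 24 urine samples in weeks 3-14. 24/84 = 29%; 84 - 24 = 60 days, and 60/84 = 71%. At least 60 AC days per patient rest on self-report or on another day's sample.

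**Bias formula.** Let pR and pA be true adherence, Sv the probability that a taken ROD dose is captured on video, Sa the probability that a taken AC dose is scored adherent, and F the probability that a missed AC dose is scored adherent. Video false positives are set to zero. Then

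observed difference = pR × Sv - [pA × Sa + (1 - pA) × F].

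**Assumed error rates.** Sv is 0.90 to 1.00. For orientation only, the feasibility study in section 1.1 had 90% of scheduled calls completed while every urine was buprenorphine positive. The lenient AC rule has Sa = 1 and F from 0 to 0.50. The strict AC rule has Sa from 0.80 to 0.90 and F = 0.

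| AC rule | True ROD, AC | Observed ROD | Observed AC | Observed difference |
|---|---|---|---|---|
| Lenient | 0.70, 0.70 | 0.63 to 0.70 | 0.70 to 0.85 | 0 to -0.22 |
| Lenient | 0.90, 0.70 | 0.81 to 0.90 | 0.70 to 0.85 | +0.20 to -0.04 |
| Strict | 0.70, 0.70 | 0.63 to 0.70 | 0.56 to 0.63 | 0 to +0.14 |
| Strict | 0.90, 0.70 | 0.81 to 0.90 | 0.56 to 0.63 | +0.18 to +0.34 |

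End points: 0.63 - 0.85 = -0.22; 0.81 - 0.85 = -0.04; 0.70 - 0.56 = +0.14; 0.81 - 0.63 = +0.18; 0.90 - 0.56 = +0.34.

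**Milder errors.** Take Sv = 0.90.

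- With F = 0.25, observed AC is 0.70 + 0.30 × 0.25 = 0.775. Equal adherence then shows as 0.63 - 0.775 = -0.145, and a true +0.20 as 0.81 - 0.775 = +0.035.
- With F = 0, the figures are 0.63 - 0.70 = -0.07 and 0.81 - 0.70 = +0.11.

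**One rule in both arms.** If sensitivity S and false-positive rate F are the same in both arms,

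[pR × S + (1 - pR) × F] - [pA × S + (1 - pA) × F] = (pR - pA) × (S - F).

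Equal adherence gives exactly 0. A real difference is shrunk but keeps its sign whenever S exceeds F. With S = 0.90 and F = 0.10, for example, 0.20 × 0.80 = +0.16.

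**The case against.** The main between-group inference is already protected. Urine levels are the stated primary comparison, they use one measure in both arms, and the only between-group power statement rests on them. Section 6.2 calls the attacked contrast exploratory, in a 40-patient test of preliminary efficacy. Urine exists for everyone, so the confounding lies in the planned scoring and not in the data. All of this stands, and it limits the point to one contrast. It does not make the planned result a direct estimate, and sections 2.1 and 3.4 rank the contrast above exploratory.

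The magnitudes are assumptions. The -22 and -4 figures need half of missed AC doses to be scored as taken, together with 10% of taken ROD doses unfilmed; no passage supports the first rate, and urine gives some check on self-report. Video false positives would raise ROD, so the ranges are not bounds. This too is fair, but the milder settings still move the result by 7 to 16.5 points.

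The remedy has real weaknesses. Dichotomised urine overlaps with the primary analysis and discards information that the linear mixed model keeps. It answers a per-visit question, and patients can dose for known visit days. A simple positive/negative rule may sit at its ceiling, as the feasibility urines suggest. A quantitative cut-off may reflect dose as well as adherence. The protocol itself expects to learn from this trial how best to use the levels. These are caveats to report with the analysis; they do not restore a comparison in which each arm has its own instrument.

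**Conclusion.** The concern holds. Followed as written, sections 3.4, 5.6 and 6.2 yield a group difference that combines treatment and measurement and can be biased in either direction. Under the assumed error rates the distortion reaches -22 to +14 points when true adherence is 70% in both arms, and a true +20 points can appear as -4 to +34. The sizes are illustrative. That instrument is tied to arm follows from the text alone.

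The primary urine-level comparison, the ROD-only video endpoint and the figures in section 6.1 are not affected. The contrast should be fixed before analysis, but the point does not undermine the trial's main comparison.

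**What to change.** In sections 3.4, 5.6 and 6.2, for the between-arm adherence-rate contrast:

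1. Classify both arms by one rule based on the creatinine-normalised buprenorphine and norbuprenorphine results from the 24 visits. Fix the rule in advance with the toxicology consultant, apply it without reference to arm, and fit the mixed-effects logistic model to the visit-level classifications.
2. Keep video adherence as the ROD endpoint and report its agreement with urine within ROD. Report AC text confirmations descriptively.
3. If the video-versus-self-report contrast is still shown, define the AC daily rule and the self-report source, label the contrast descriptive, and show how it moves over a range of error rates.
4. Delete the claim of a direct estimate in 3.4 and 5.6.
5. Give the contrast one status in 2.1, 3.4 and 6.2.

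**Cost.** No new data; some analysis work and a cut-off that must be justified, because section 4 allows doses to be individualised. Resolution drops from 84 days to 24 visits, and the analysis partly overlaps with the primary one. The common rule removes the built-in bias only if its error rates are similar in the two arms; dosing timed to visits, or different doses by arm, could break that. The report should say so.
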